Appendix 2.3. DAS 28-3 (CRP)

The Disease Activity Score (DAS) is a derived measurement with differential weighting given to each component. DAS 28-3 (CRP) will be calculated from measurements made at all visits (Madsen, 2011).⁷

The components of the DAS 28-3 arthritis assessment are:

Tender/Painful Joint Count (28);

Swollen Joint Count (28);

C-Reactive Protein (CRP in mg/L).

The 28 joint counts include the following joints: shoulders, elbows, wrists, metacarpophalangeal joints (MCP), proximal interphalangeal joints (PIP), and knees.

$$\text{DAS28-3(CRP)} = [0.56 * \text{sqrt}(\text{TJC28}) + 0.28 * \text{sqrt}(\text{SJC28}) + 0.36 * \ln(\text{CRP}+1)] * 1.10 + 1.15$$

where sqrt() refers to the square root, and ln() refers to the natural logarithm.

Any missing component will result in DAS28-3 (CRP) as missing. A higher score of DAS28-3 (CRP) represents a more severe disease activity.

Appendix 2.4. PsA Response Criteria (PsARC)

The PsARC will be collected/derived at all visits in addition to the ACR response criteria. The PsARC consists of 4 measurements:

Tender joint count (68);

Swollen joint count (66);

Physician's Global Assessment of Arthritis (VAS);

Patient's Global Assessment of Arthritis (VAS).

The same tender/painful joint count and swollen joint count used for ACR response criteria will be applied to the PsA Response Criteria. In order to be a 'PsARC responder', subjects must achieve improvement in 2 of 4 measures, one of which must be joint pain or swelling, without worsening in any measure.

Specifically, the PsARC response is defined as improvement in two of the following 4 criteria, one of which must be joint pain or swelling, without worsening in any measure: (1) $\geq 20\%$ improvement in Physician's Global Assessment of Arthritis (VAS); (2) $\geq 20\%$ improvement in Patient's Global Assessment of Arthritis (VAS); (3) $\geq 30\%$ improvement in tender joint count (68); and (4) $\geq 30\%$ improvement in swollen joint count (66) (Gottlieb et al 2008).⁵

Methods in calculating percent change from baseline when baseline value of any component is equal to 0 can be found in [Appendix 2.1](#).

If values in any of the components at a timepoint are missing, the components that are not missing are used to determine the response status. If one could not determine the response status in the presence of missing components at the timepoint, then PsARC response will be considered as missing. The VAS data will need to be rescaled prior to any calculation ([Section 6](#)).

Appendix 2.5. PsA Joint Activity Index (PsAJAI)

The PsA Joint Activity Index (PsAJAI) is a weighted sum of $\geq 30\%$ improvement in the 7 core measures of the ACR with weights of 2 given to the joint count measures (JNT, defined below), CRP and the physician's global assessment of disease activity (MDGDA). Weights of 1 are given to the remaining $\geq 30\%$ improvement measures including patient's assessment of arthritis pain (PAIN), patient's global assessment of Arthritis (PtGDA) and HAQ-DI (Gladman et al 2010).⁴ The values are summed to get a score out of 9 (range 0-9). The score is calculated as follows:

$$\text{PsAJAI} = 2 \times 30\% \downarrow \text{JNT} + 2 \times 30\% \downarrow \text{CRP} + 2 \times 30\% \downarrow \text{MDGDA} + 30\% \downarrow \text{PtGDA} + 30\% \downarrow \text{PAIN} + 30\% \downarrow \text{HAQ-DI}.$$

The formula contains indicator functions. For example, if a subject has a $\geq 30\%$ improvement in CRP, the term “ $30\% \downarrow \text{CRP}$ ” will be set to 1 in the above formula; otherwise it is set to 0. For JNT, “ $30\% \downarrow \text{JNT}$ ” will be set to 1 only if BOTH $\geq 30\%$ improvement/reduction in tender/painful joints (68) AND $\geq 30\%$ improvement/reduction in swollen joints (66), otherwise “ $30\% \downarrow \text{JNT}$ ” will be set to 0.

Methods in calculating percent change from baseline when baseline value of any component is equal to 0 can be found in [Appendix 2.1](#).

PsAJAI is set to missing if any of the 7 components (JNT is comprised of tender and swollen joint counts) is missing.

The VAS data will need to be rescaled prior to any calculation ([Section 6](#)).

Appendix 2.6. Disease Activity Index for Reactive Arthritis/Psoriatic Arthritis (DAREA/DAPSA)

DAREA/DAPSA (Schoels et al 2010)¹⁰ is a composite instrument to assess peripheral joint involvement that is based upon numerical summation of 5 variables of disease activity: tender/painful joint count + swollen joint count (using SJC66/ TJC68 assessments), patient's global assessment of Arthritis (PtGA in cm), patient's assessment of Arthritis Pain (PAIN in cm) and CRP (in mg/dL). Since DAREA/DAPSA reflects domains found important in PsA, it has been proposed to serve as a Disease Activity Index for Psoriatic Arthritis (DAPSA). DAREA/DAPSA is calculated as follows:

$$DAREA/DAPSA = SJC66 + TJC68 + PtGA + PAIN + CRP.$$

Any missing component will result in DAREA/DAPSA as missing.

The VAS data will need to be rescaled prior to any calculation ([Section 6](#)).

Appendix 2.7. Composite Psoriatic Disease Activity Index in Psoriatic Arthritis (CPDAI)

CPDAI (Mumtaz et al 2011)⁸ is a composite psoriatic disease activity index incorporating 5 domains including joint disease, skin involvement, enthesitis, dactylitis and spinal disease. For dactylitis, a simple dactylitic digit count was applied. For enthesitis, the Leeds enthesitis index (LEI) was used. For spinal involvement, the Bath Ankylosing Spondylitis Disease Activity Index (BASDAI) and the Ankylosing Spondylitis Quality of Life (ASQOL) were used. In addition, the Dermatology Quality of Life Index (DLQI) was used as a measure of the impact of skin disease. Using these instruments, and ranges of values based upon literature review, disease activity under each domain was graded as none, mild, moderate and severe giving a range of attainable CPDAI scores of between 0 and 15. A higher CPDAI score indicates a higher disease activity.

Composite Psoriatic Disease Activity Index (CPDAI) score total 0-15

	Not involved (0)	Mild (1)	Moderate (2)	Severe (3)
Peripheral arthritis		≤4 Joints (count a joint that is swollen and/or tender); normal function (HAQ-DI ≤0.5)*	≤4 Joints but function impaired; or >4 joints, normal function	> 4 Joints and function impaired
Skin disease		PASI ≤10 and DLQI ≤10	PASI ≤10 but DLQI >10; or PASI >10 but DLQI ≤10	PASI >10 and DLQI >10
Enthesitis		≤3 Sites; normal function (HAQ-DI ≤0.5)*	≤3 Sites but function impaired; or >3 sites but normal function	>3 Sites and function impaired
Dactylitis		≤3 Digits; normal function (HAQ-DI ≤0.5)*	≤3 Digits but function impaired; or >3 digits but normal function	>3 Digits and has function impaired
Spinal disease		BASDAI ≤4; normal function (ASQoL ≤6)	BASDAI >4 but normal function; BASDAI ≤4 but function impaired	BASDAI >4 and function impaired

**Health assessment questionnaire-disability index (HAQ-DI) only counted if clinical involvement of domain (joint/ethesis/dactylitis) present. DLQI or ASQoL only counted if clinical involvement of domain (ie, PASI>0 or BASDAI>0) present.*

Explicitly, each disease dimension will be scored as follows (0=not involved, 1=mild, 2=moderate, 3=severe). For evaluating peripheral arthritis score (D1 below), if a joint is swollen and/or tender, it is only counted once.

D1. Peripheral arthritis scoring

	HAQ-DI	
Joints (swollen or tender)	≤0.5	>0.5
0	0	0
1 to 4	1	2
>4	2	3

D2. Skin disease scoring

	DLQI	
PASI	≤10	>10
0	0	0
0< to ≤10	1	2
>10	2	3

D3. Leeds enthesitis scoring

	HAQ-DI	
Sites	≤0.5	>0.5
0	0	0
1 to 3	1	2
>3	2	3

D4. Dactylitis scoring

	HAQ-DI	
Digits	≤0.5	>0.5
0	0	0
1 to 3	1	2
>3	2	3

D5. Spinal disease scoring

	ASQol	
BASDAI	≤6	>6
0	0	0
0< to ≤4	1	2
>4	2	3

$$CPDAI = D1 + D2 + D3 + D4 + D5.$$

CPDAI will be set as missing if any of the component score is missing. Per the study protocol, PASI should only be performed if ≥3% of subject's BSA is affected at baseline, thus CPDAI will be set as missing and excluded from any analysis for any subject (the entire subject) whose baseline BSA is <3%.

Appendix 2.8. Minimal Disease Activity (MDA) Response

A psoriatic arthritis patient is defined as having Minimal Disease Activity (MDA, yes/no) when the patient meets ≥5 of the 7 following criteria: 1) tender/painful joint count ≤1; 2) swollen joint count ≤1; 3) PASI score ≤1 or BSA ≤3%; 4) patient assessment of Arthritis Pain (VAS) ≤15 mm; 5) patient's global arthritis assessment (VAS) ≤20 mm; 6) HAQ-DI score ≤0.5; 7) tender enthesal points (using Leeds Enthesitis Index) ≤1.

If < 5 non-missing component criteria are satisfied and at least one of the remaining component criteria is missing, then MDA response is set to be as missing.

The VAS data will need to be rescaled prior to any calculation ([Section 6](#)).

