7. HANDLING OF MISSING VALUES

For the SF-36v2, ASQOL, DLQL, EQ-5D-3L, BASDAI, WLQ, PsA-HCRU, and FACIT-F instruments, rules suggested by the developers of these will be followed in calculating scores when individual question/items may be missing. If these rules are not enough for calculating a score, then the endpoint will be considered to have a missing value. Missing values in any of the endpoints will not be imputed when summarizing these endpoints using descriptive statistics. See [Appendix 2](#) for additional details for the calculation of endpoints, including handling of missing item values in the calculation.

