8.1.2. Analyses for Categorical Data

The data for all categorical endpoints (including binary) will be summarized by contingency tables that show the counts/frequency in the various categories at each time point. For some categorical endpoints, such as the presence or severity of adverse events, contingency or frequency tables will consider the data over the entire duration of the study and will not be constructed at each time point.

Normal approximation will be used for the construction of confidence interval (CI) for the responder rate over time. Let N be number of subjects assessed at each visit and n be number of responders, and $p_{\text{obs}} = n/N$ be the observed responder rate, then the two-sided 95% CI will be formed by $p_{\text{obs}} \pm 1.96 \times \text{squared root of } [p_{\text{obs}} \times (1 - p_{\text{obs}}) / N]$.

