8.2.2. Analysis of Secondary and Other Efficacy/Health Outcome Endpoints

Efficacy analysis will only include the data collected in the main LTE study.

Contingency/frequency tables as described in [Section 8.1.2](#) will summarize:

- ACR20, ACR50 and ACR70 response rate at all time points.

In addition, the ACR response rates will be displayed at all time points by the qualifying study. As a sensitivity analysis to using the baseline values from the qualifying study for all subjects, one will also provide tables of ACR response rates in which baseline is the baseline visit for A3921092 for patients whose enrollment are out of 14-day window.

- Psoriatic Arthritis Response Criteria (PsARC) response at all timepoints.
- Psoriasis Area and Severity Index 75 (PASI75) response, ie, the proportion of subjects achieving at least a 75% reduction in PASI relative to baseline for subjects with baseline BSA \geq 3% and baseline PASI $>$ 0 (see [Section 5.4.1](#)).
- Presence of dactylitis at all timepoints for subjects with baseline DSS $>$ 0.
- HAQ-DI response rates (2 endpoints: (decrease of \geq 0.30 and decrease of \geq 0.35) at all timepoints for subjects with baseline HAQ-DI \geq 0.30 and HAQ-DI \geq 0.35, respectively) (see [Section 5.4.1](#)).
- Minimal Disease Activity (MDA) at all timepoints.

Descriptive statistics as described in [Section 8.1.1](#) will be tabulated for:

- ACR response criteria components (Δ in HAQ-DI, CRP, Patient's Assessment of Arthritis Pain, Patient's Global Assessment of Arthritis, Physician's Global Assessment of Arthritis, swollen joint count, tender/painful joint count) at all timepoints.

In addition, the descriptive statistics for Δ HAQ-DI scores will be displayed at all timepoints by the qualifying study. As a sensitivity analysis to using the baseline values from the qualifying study for all subjects, one will also provide tables of

descriptive statistics in which baseline is the baseline visit for A3921092 for patients whose enrollment are out of 14-day window.

- *Physician's Global Assessment of Psoriasis (Δ PGA-PsO) response at all timepoints* for subjects with baseline PGA-PsO>0 (see [Section 5.4.1](#)).
- *PASI and PASI component scores (% Δ PASI and its clinical signs component scores)* at all timepoints for subjects with BSA \geq 3% and baseline PASI>0 (see [Section 5.4.1](#)).
- *BSA (% Δ BSA) at all timepoints* for subjects with baseline BSA>0 (see [Section 5.4.1](#)).

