Appendix 2. Further Definition of Endpoints

Appendix 2.1. ACR Assessments

The American College of Rheumatology's definition for calculating improvement in RA (ACR20) is calculated as a $\geq 20\%$ improvement in tender and swollen joint counts and $\geq 20\%$ improvement in 3 of the 5 remaining ACR-core set measures: patient and physician global assessments, pain, disability, and an acute-phase reactant. Similarly, ACR50 and 70 are calculated with the respective percent improvement. This efficacy measurement will be made at every study visit. The specific components of the ACR Assessments that will be used in this study are:

Tender/Painful Joint count (68);

Swollen Joint Count (66);

Patient's Assessment of Arthritis Pain (VAS);

Patient's Global Assessment of Arthritis (VAS);

Physician's Global Assessment of Arthritis (VAS);

C-Reactive Protein (CRP in mg/L);

Health Assessment Questionnaire – Disability Index (HAQ-DI).

If the value in any of the components at a timepoint is missing, the component variables that are not missing will be used to determine the response status. As a general principle, if there are sufficient non-missing components to determine whether the ACR endpoint is a response or non-response, then ACR endpoint is not missing, else if the available non-missing components are not sufficient to determine the response status of ACR endpoint then it is considered missing.

In order to avoid numerical difficulty, if the baseline value of any component is equal to 0, the following algorithm will be used in evaluating the percent change from baseline:

1. If change from baseline is also equal to 0, then percent change from baseline is set to be 0%;
2. If change from baseline is > 0 , then percent change from baseline is set to be 999999%.

These percentages will be used to derive the ACR endpoints. Change from baseline cannot be < 0 since none of the components should have negative value.

Lower limit of quantification (LLOQ) for CRP is 0.020 mg/dL (or 0.200 mg/L). Any CRP value below the LLOQ will be reported as " <0.020 " in database and will be set to 0.019 mg/dL (0.190 mg/L) and used in analyses throughout. The unit for CRP will be mg/dL or mg/L depending on endpoint of interest. The upper limit of the normal range is 2.87 mg/L.

The VAS data will need to be rescaled prior to any calculation ([Section 6](#)).

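### In the LTE, the MDA missing-data rule drops visits at which MDA is already ruled out, so no incomplete visit can be scored as a non-response

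*SAP*

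**What the plan says.** SAP Appendix 2.8 classes a subject as having MDA "when the patient meets ≥5 of the 7 following criteria". Its missing-data rule covers subjects with fewer than 5 criteria met: if any other criterion is unobserved, the endpoint becomes missing ("and at least one of the remaining component criteria is missing, then MDA response is set to be as missing"). The number of criteria observed to fail plays no part.

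Three LTE provisions carry this into the reported rate:
- SAP Section 7: "Missing values in any of the endpoints will not be imputed when summarizing these endpoints using descriptive statistics".
- SAP Section 8.1.2 defines the responder rate as n/N: "Let N be number of subjects assessed at each visit and n be number of responders".
- SAP Section 8.2.2 lists "Minimal Disease Activity (MDA) at all timepoints" under that method.

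The SAP treats its other composite responses differently. For ACR (Appendix 2.1), "if there are sufficient non-missing components to determine whether the ACR endpoint is a response or non-response, then ACR endpoint is not missing". For PsARC (Appendix 2.4), the endpoint is missing only "If one could not determine the response status in the presence of missing components at the timepoint". SAP Section 1 records that version 3 recast the ACR rule as a general principle. No reason is given for treating MDA differently.

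In the methotrexate-withdrawal sub-study (SAP Appendix 6, Section 6), a missing binary response counts as non-response.

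**The concern.** Five of seven criteria are needed, so three observed failures settle the answer: at most four can be met. Appendix 2.8 nevertheless sets such a subject to missing, and in the LTE missing subjects leave both numerator and denominator. Incomplete visits that reach 5 are kept, while incomplete visits that cannot reach 5 are removed. This is neither a complete-case rule, which would drop both, nor a determinable-status rule, which would keep both.

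What is at stake is the long-term MDA rate shown at each visit. The LTE is displayed as one flexibly dosed cohort (SAP Section 8.2), so the rate will be read as an absolute figure.

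**Working it through.** The documents give no MDA rate and no missingness rate, so there is no planned figure to reproduce. The check has a logical part, which needs no assumptions, and a sizing part, which does.

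**1. Classification.** Let S = criteria met, F = criteria failed and M = criteria missing, with S + F + M = 7. MDA is certain if S ≥ 5, impossible if F ≥ 3 (since 7 − 3 = 4 < 5), and otherwise undetermined.

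| M | Response certain | Undetermined | Non-response certain | SAP result for the last two |
|---|---|---|---|---|
| 1 | S = 5 or 6 | S = 4 | S = 0 to 3 | missing |
| 2 | S = 5 | S = 3 or 4 | S = 0 to 2 | missing |
| 3 | none | S = 2 to 4 | S = 0 or 1 | missing |

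**2. Count of all patterns.** There are 3^7 − 2^7 = 2,187 − 128 = 2,059 patterns with at least one criterion missing.
- Certain responses: 21 × 3 + 7 × 1 = 70. All are kept as responses.
- Certain non-responses: 939 patterns have F ≥ 3, of which 99 are complete, leaving 840. All are set to missing.
- Undetermined: 2,059 − 70 − 840 = 1,149. All are set to missing.

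No incomplete pattern is ever scored as a non-response.

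**3. Comparison with the ACR/PsARC principle.** Let n be the responders, N the subjects whose status can be determined, and k the certain non-responders among the incomplete visits. The determinable-status rate is n/N and the Appendix 2.8 rate is n/(N − k). The second is higher whenever k > 0 and n > 0, whatever the missingness mechanism.

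**4. Illustration (invented counts).** Take 100 subjects. Ninety are complete, with 30 responders. Ten have one criterion missing: 2 have at least 5 met, 7 have at least 3 failed, and 1 is undetermined.
- Appendix 2.8: 32/92 = 34.8%.
- Determinable status: 32/99 = 32.3%.
- Missing as non-response: 32/100 = 32.0%.

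**5. Size against the true rate.** Assumptions, none of them from the documents: seven exchangeable criteria under a beta-binomial model, within-subject correlation 0.3 or 0.5, true MDA rate t = 35%, and M criteria missing completely at random at a fraction m of visits. Let q be the chance that an incomplete visit still shows at least 5 met, and r the chance that it shows at least 3 failed.

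Appendix 2.8 rate = [t(1 − m) + mq] / [(1 − m) + mq].

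Determinable-status rate: the same numerator over (1 − m) + m(q + r).

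At correlation 0.3 and m = 10%, the Appendix 2.8 rate is:
- M = 1, q = 0.258: (0.315 + 0.0258)/(0.90 + 0.0258) = 36.8%.
- M = 2, q = 0.142: (0.315 + 0.0142)/(0.90 + 0.0142) = 36.0%.
- M = 3, q = 0: 0.315/0.90 = 35.0%.

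Across both correlations, with t = 35%:

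| Criteria missing | m = 2% | m = 5% | m = 10% |
|---|---|---|---|
| 1 | 35.3–35.4% | 35.9–36.0% | 36.8–37.0% |
| 2 | 35.2–35.3% | 35.5–35.7% | 36.0–36.4% |
| 3 | 35.0% | 35.0% | 35.0% |

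At m = 10% with one criterion missing, the excess is 1.2 to 1.4 points for a true rate of 20% and 2.1 to 2.3 points for a true rate of 50%.

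The determinable-status rule is not exact either. At m = 10% and t = 35% it gives 34.6–34.7% with one criterion missing. With three missing, r = 0.409 or 0.496, and it gives 0.315/0.9409 = 33.5% or 0.315/0.9496 = 33.2%.

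**The case against.** The strongest case on the other side has four parts.

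**The direction is not fixed.** A reader might infer that the rule always inflates the MDA rate, or always favours treatment. The documents do not support that. Protocol Sections 6.2 and 7.5 say that a questionnaire which cannot be completed at the clinic visit is not to be given. Pain, patient global and HAQ-DI are three of the seven criteria and are collected together. If all three are missing, no responder can be identified, the rule reduces to complete-case analysis, and under random missingness it is unbiased. If subjects with missing criteria were much more often true responders, the rate could even read low. This stands, and limits the claim to the comparison with the SAP's own principle.

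**The size is probably modest.** Missing single joints are filled in (SAP Appendix 5), HAQ-DI tolerates two missing domains (Appendix 2.2), and either PASI or BSA can satisfy the skin criterion. Routes to a single missing criterion remain, such as one enthesitis site not done, which voids the Leeds index (SAP Section 6.2), or a missing VAS. This stands: nothing in the documents supports a high missingness rate.

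**The consequence is limited.** MDA is among the other endpoints of the LTE (SAP Section 6.3), which has no hypotheses or decision rules. A reader might also infer that the sub-study, where MDA is secondary and compared between arms, is affected. It is not: counting missing as non-response scores every certain non-responder correctly there.

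**The repair is not neutral.** Certain non-responders return to the denominator while undetermined visits stay out, so the repaired rate can read low, as step 5 shows. This also stands, and is why the fix includes a count and a sensitivity rate.

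None of this gives a reason to discard observed non-responses.

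**Conclusion.** The rule is wrong as written. It sets to missing subjects whose non-response is already established, and it departs without explanation from the principle the SAP uses for ACR and PsARC. The LTE MDA rate will be at least as high as under that principle. This part rests on arithmetic alone.

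The effect against the true rate is conditional. With one criterion missing at random and a true rate near 35%, the excess is about 0.4, 1 and 2 points at 2%, 5% and 10% of visits. With two missing it is somewhat over half of that, and with pain, patient global and HAQ-DI all missing it is about zero. The missingness rates, the correlation and the true rate are all assumed.

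No test, primary conclusion or between-arm comparison is touched. The correction is worth making because the selection is avoidable and the published rate will be read at face value.

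**What to change.** Replace the missing-data sentence in SAP Appendix 2.8 with: *MDA = yes if at least 5 criteria are met; MDA = no if at least 3 non-missing criteria are not met; otherwise missing.* In the LTE tables, show the number of undetermined subjects at each visit, and give a sensitivity rate that counts missing as non-response among subjects seen at that visit.

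The cost is one SAP sentence, one line of derivation code and two more entries per visit in the MDA table. The reported rate becomes slightly less favourable, and it can read slightly low where several criteria are missing together. The undetermined count lets a reader see whether that applies.
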